The sample-size calculation was based on the assumption of a SSM of 35.8 kPa during treatment and a detectable increase of 35.0% (48.3 kPa) while supressing one dose of carvedilol (1). We considered standard deviation as 19.2 kPa, an alpha of .05 and a power of .80. We also assumed that 10% of enroled patients might fulfil further exclusion criteria, by not following the study proposed regimen, totalling 33 patients needed to enrol in the study.

Data Analysis

Categorical variables were described with absolute and relative (%) frequencies and continuous variables were described with means and standard deviations (SD) when approximately normally distributed or with median an interquartile range (IQR) otherwise. Results from the SSM evaluation through TE at appointment were compared with the values measured before introduction of carvedilol and in the previous TE evaluation within 3 months, using paired t-tests. Further comparisons between SSM at appointment and within the previous 3 months were made stratifying for aetiology of portal hypertension, *D'Amico* classification, the Model MELD scores, Child-Pugh score, and carvedilol daily dosage. For the described analysis, aetiology was divided in alcoholic cirrhosis and non-alcoholic cirrhosis; in quartiles for MELD and Child-Pugh; and in above and below the median for carvedilol daily usage. The same procedure was repeated for LSM.

Data analysis was performed using R version 4.3.0 (R Foundation for Statistical Computing, Vienna, Austria). 95% confidence intervals (CI) for point estimates were calculated. P-values <.05 were considered statistically significant.

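### No primary test is declared, and one unadjusted .05 rule covers roughly 28 to 44 tests, although the sample size points to a single SSM comparison

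*SAP*

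**What the plan says.** The protocol's Objectives refer to acute effects of carvedilol posology and name no measure or comparison. Its Study design lists SSM and LSM comparisons without ranking them, and there is no endpoint section.

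The SAP's Sample Size section is built on one contrast, the "assumption of a SSM of 35.8 kPa during treatment and a detectable increase of 35.0% (48.3 kPa) while supressing one dose of carvedilol". It continues: "We considered standard deviation as 19.2 kPa, an alpha of .05 and a power of .80". The total is given as "totalling 33 patients needed to enrol in the study".

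The Data Analysis section sets out:

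- two paired t-tests for SSM at the appointment, one against the value before carvedilol and one against the TE within the previous 3 months;
- further comparisons, against the on-treatment TE only, stratified by aetiology (two groups), D'Amico classification (number of groups not given), MELD, Child-Pugh and carvedilol dose, the last three split "in quartiles for MELD and Child-Pugh; and in above and below the median for carvedilol daily usage";
- then: "The same procedure was repeated for LSM".

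The closing rule is "P-values <.05 were considered statistically significant". There is no hierarchy, no multiplicity adjustment and no exploratory label. 95% confidence intervals for point estimates are planned.

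**The concern.** The .05 rule is stated without limit, so it reaches an LSM result or a single stratum just as it reaches the comparison that was powered. A plan followed to the letter would allow a p-value below .05 in one quartile of one score to be called a significant effect of omitting the dose. With about 30 evaluable patients a quartile holds 7 or 8 people. A significant result in one stratum and not in its neighbour also does not show that the strata differ.

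The two SSM comparisons answer different questions. A rise above the on-treatment value suggests that effect is lost after the omitted dose. A value still below the pre-carvedilol reading suggests that effect is retained. If neither is designated as primary, the leading result can be chosen after the data are seen.

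**Working it through.** **1. Which comparison was powered.** Inputs from the SAP's Sample Size section: 35.8 to 48.3 kPa, a difference of 12.5 kPa; SD 19.2 kPa; alpha .05, sidedness not stated; power .80; 10% post-enrolment exclusion; 33 to enrol. A one-sided two-sample formula gives n = 2 × 19.2² × (1.645 + 0.842)² / 12.5² ≈ 29.2, so 30, and 30 × 1.10 = 33. A two-sided paired t-test also needs 30 if an unstated within-patient correlation of about 0.25 is assumed. On either route the calculation concerns one contrast only, SSM on treatment versus after the omitted dose, with about 30 evaluable patients. How 33 was derived is a separate question.

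**2. How many tests share the .05 rule.** Assume one paired test per stratum. Let m be the number of MELD versions used for stratifying and D the number of D'Amico strata. Each measure then has 2 overall tests, 2 for aetiology, 4 for Child-Pugh, 2 for dose, 4m for MELD and D for D'Amico. For two measures:

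k = 2 × (2 + 2 + 4 + 2 + 4m + D) = 2 × (10 + 4m + D)

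| MELD versions | D'Amico strata counted | All tests | Omission tests (k − 2) |
|---|---|---|---|
| 1 | 0 | 28 | 26 |
| 1 | 2 | 32 | 30 |
| 2 | 0 | 36 | 34 |
| 2 | 4 | 44 | 42 |

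The last column removes the two comparisons with pre-carvedilol values, which do not test omission of the dose. The rows with D = 0 leave out the planned D'Amico tests because their number is not given. The SAP's Data Collection section says that MELD-Na and MELD 3.0 are both collected; Data Analysis does not say whether both are used for stratifying.

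**3. False-positive risk if omitting the dose has no effect.**

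- Powered SSM test alone: 5%.
- Two overall omission tests, SSM and LSM versus on treatment: 1 − 0.95² = 9.75% if independent; about 7-10% simulated.
- All omission tests, if independent: 1 − 0.95^26 = 74% to 1 − 0.95^42 = 88%. These are too high, because the strata re-use the same patients.
- All omission tests, simulated with nested strata, 30 patients and SSM-LSM correlation 0 to 0.8: about 56-80% for at least one p<.05.
- Expected number of false positives, which does not depend on correlation: 26 × 0.05 = 1.3 to 42 × 0.05 = 2.1.

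The simulation correlations are assumptions; the documents give none.

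**The case against.** The best defence is that a hierarchy is implied. The sample size rests on one contrast, the objective about acute effects fits it, the stratified comparisons are introduced as further ones, and LSM follows as a repetition. This stands in part: it would be wrong to infer that the plan intends all tests to have equal standing. But Data Analysis does not declare the hierarchy, and the significance rule ignores it.

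Three stronger readings are tempting and are not supported.

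- *A false-positive headline result is likely.* The 56-80% figure is the chance that any one of many tests, nearly all of them subgroup tests, falls below .05. It becomes a headline risk only if such a result is promoted, and the SAP has no rule promoting it. The powered comparison carries 5%.
- *There are at least 36 tests.* That needs both MELD versions as separate stratifiers, or one version with four D'Amico strata. The SAP settles neither, and ties in the Child-Pugh score could merge quartiles and lower the count.
- *The four overall tests carry 1 − 0.95⁴ = 18.5%.* This needs every null to be true. Patients whose SSM fell by less than 10% are excluded, so on-treatment SSM should lie below the pre-carvedilol value. If omission does nothing, appointment SSM should still differ from the pre-carvedilol value, and p<.05 there would not be a false positive.

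It is also fair to say that strata of 7 or 8 arise only from the quartile factors. Dose halves would hold about 15 patients, and the aetiology group sizes are unknown.

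**Conclusion.** The concern holds, in a limited form. No primary test is declared, and an unadjusted .05 rule covers roughly 28 to 44 tests. If omission has no effect, the false-positive risk is 5% for the powered SSM test, about 7-10% for the two overall omission tests, and about 56-80% for at least one of the 26 to 42 omission tests.

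These figures assume one test per stratum, about 30 evaluable patients, no true effect on either measure and an SSM-LSM correlation between 0 and 0.8. The 5% is the nominal level of the test. It takes no account of any selection on the on-treatment reading itself, since the documents do not say which reading decided responder status. The conclusion does not turn on the exact count; that the count cannot be fixed from the SAP is part of the gap.

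**What to change.** In Data Analysis, state that the primary analysis is the paired change in SSM from the on-treatment TE (within the previous 3 months) to the appointment TE, tested at two-sided alpha .05, and limit the .05 sentence to that test. Label the LSM comparisons and the comparisons with pre-carvedilol values as secondary, and all stratified results as exploratory, reported as estimates with the 95% confidence intervals already planned. It would help to state in the same place which MELD version defines the quartiles and how D'Amico classes are grouped.

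An ordered testing sequence or a multiplicity adjustment for the secondary comparisons would also answer the point. For 36 tests a Bonferroni threshold would be 0.05/36 = 0.0014, which is severe for a study of this size, so labelling is the more practical choice.

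The cost is a few sentences, with no new patients, data or procedures. The downside is that secondary and stratified results can no longer be claimed as significant.
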